6.3.2. Per Protocol (PP) Population

The PP population will include all subjects who met all inclusion/exclusion criteria, complied with the assigned study product, complied with the daily diary, and were followed up until resolution of symptoms, or completed 180 days without resolution of symptoms.

A subject is considered to be compliant with the assigned study product if he/she takes at least 75% of the scheduled doses through 28 days and does not receive additional nitazoxanide (defined as in [Section 3.3](#)) before their primary outcome is observed. A subject is compliant with the daily diary if he/she is missing no more than 1.5/7 days per week over the first 8 weeks (Day 1 through Day 60).

This analysis set will be used for all efficacy analyses and will be considered secondary to analyses conducted in the mITT population.

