11 STATISTICAL CONSIDERATIONS

11.1 Study Hypotheses

A formal hypothesis test is planned to compare nitazoxanide to placebo with respect to the primary efficacy outcome measure. The time from randomization until clinical resolution of Norovirus for at least 48 hours through 180 days will be compared between the two study arms.

The null hypothesis is that there is no difference in time until clinical resolution between study arms, with a two-sided alternative. The test for primary efficacy hypothesis will be conducted using a Log-Rank test at the 5% two-sided level of significance.

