5. SAMPLE SIZE CONSIDERATIONS

Sample size calculations assume a 50% reduction in the median duration of diarrhea for the nitazoxanide-treated group compared to those receiving placebo. The median diarrhea duration for the placebo group is assumed to be 135 days, while the median diarrhea duration for the treatment group is assumed to be 67.5 days. Given these assumptions, a sample size of 64 subjects in each arm (128 total) is required to achieve 90% power using the Log-Rank test. Accounting for a 20% attrition rate, final sample size will be 80 in each arm (160 total).

Though discouraged, the protocol allows for subjects in either study group to receive additional nitazoxanide after 28 days. Under the assumptions of treatment efficacy, additional treatment received by placebo subjects would reduce the median duration of symptoms for the placebo group to be closer to that of the nitazoxanide-treated group. It is assumed that subjects who would have the worst study outcomes (longest time to clinical resolution of diarrhea) will be the most likely to receive additional treatment. Subjects receiving additional treatment will be imputed as having the worst outcome (time to resolution censored at 180 days). Accounting for this imputation method, the power attained for the primary comparison was computed via simulation (R version 3.0.3). Estimated power is displayed in [Table 2](#), varying the proportion of subjects in each study group who receive additional treatment.

For example, if 15% of placebo subjects receive nitazoxanide, and 5-10% of subjects in the nitazoxanide-treated group receive additional treatment, the power is estimated to be 91.2%. Note that implausible scenarios (where substantially more nitazoxanide subjects receive additional treatment than do placebo subjects) have been omitted from the table.

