6.5. Missing Data

All attempts were made to collect all data per protocol. Imputations will only be performed for missing daily diary data as it relates to the primary endpoint. Missing daily diary data for the primary endpoint will be handled as follows:

- Data that are missing after a subject has reached clinical resolution will not affect the primary time to event analysis and therefore will be ignored
- Subjects who drop out, are lost to follow-up, withdraw consent, or otherwise stop completing daily diary entries before clinical resolution will be censored on the day of their last completed diary
- Subjects with a gap in outcome data prior to clinical resolution will be handled depending on their last completed diary entry and their next completed diary entry:
 - If the last completed diary entry and the next completed diary entry have the same outcome (i.e., they are still symptomatic on both days or they have no symptoms on both days), then the gap will be imputed with the same outcome
 - If this imputation results in the subject being defined as having clinical resolution during this gap, their time to resolution will be the median of the interval
 - If the last completed diary entry and the next completed diary entry have different outcomes (i.e., the last one is symptomatic and the next one is asymptomatic, or vice versa), then the gap will be imputed with the symptomatic outcome (no resolution).

[Table 3](#) provides summary statistics (n, mean, median, standard deviation, minimum, and maximum) of the number of imputed diary days per subject given the above imputation rules and the number of overall missing diary days per subject. The above method will be considered the primary imputation method for the primary endpoint. In addition, a sensitivity analysis on the primary endpoint will be conducted using worst case scenario for subjects who drop out, are lost to follow-up, withdraw consent, or otherwise stop completing

daily diary entries before clinical resolution. These subjects will be censored at 180 days (i.e., assuming resolution of symptoms occurred after Day 180). [Listing 9](#) provides subject-level details for the number of diaries missed by week.

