8.1.1. Supplemental and Sensitivity Analyses

The primary analysis will be repeated in the Per Protocol analysis population, where subjects who were not compliant with the diary and/or treatment will be excluded from the analysis. The tabular and graphical summaries described in the previous section will be replicated for this Per Protocol analysis ([Table 16](#), [Figure 4](#), and [Figure 7](#)).

Sensitivity analyses will be performed using the stratified Cox proportional hazards model on both the mITT population and PP population using the worst-case scenario imputation method for subjects who drop out, are lost to follow-up, withdraw consent, or otherwise stop completing daily diary entries before clinical resolution ([Table 17](#)). These subjects will be censored at 180 days. Kaplan-Meier curves for each treatment arm will be presented ([Figure 5](#)). Kaplan-Meier curves for each treatment arm and duration of symptoms strata will be displayed in [Figure 8](#).

The primary analysis will be repeated on the mITT population using the subgroups defined in Section [6.4](#) ([Table 18](#)). A sensitivity analysis will be performed using the stratified Cox proportional hazards model on the mITT population with stratification based on subjects with less than 2 missing diaries per week versus

those with 2 or more missing diaries per week ([Table 19](#)). Kaplan-Meier curves for each treatment arm and diary compliance strata will be presented in [Figure 9](#).

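### The per-protocol set drops subjects who leave unresolved before Day 180 but not those who leave after resolving, so membership depends on the primary outcome

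*SAP*

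**What the plan says.** SAP 6.3.2, repeating protocol 11.4.2, sets four conditions for the PP set: eligibility, compliance with study product, compliance with the diary, and a follow-up condition. Under the last, subjects must be those who "were followed up until resolution of symptoms, or completed 180 days without resolution of symptoms". The diary condition is "missing no more than 1.5/7 days per week over the first 8 weeks (Day 1 through Day 60"), with no exception once a subject has resolved. PP results "will be considered secondary to analyses conducted in the mITT population".

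For the primary endpoint, SAP 6.5 keeps dropouts in the analysis: anyone who drops out or stops the diary "before clinical resolution will be censored on the day of their last completed diary".

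SAP 8.1.1 then uses the PP set twice. "The primary analysis will be repeated in the Per Protocol analysis population", and the dropout sensitivity analysis is run "on both the mITT population and PP population using the worst-case scenario imputation method". SAP 8.2 also uses the PP set for both virologic outcomes. SAP Table 7 has a PP exclusion row for incomplete follow-up, and its note ranks that reason last.

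**The concern.** A per-protocol set should select on adherence. The follow-up clause selects on whether the event has happened. An unresolved subject who leaves at Day 90 is deleted with 90 days of event-free time, while a subject who resolved at Day 80 and left at Day 90 meets the criterion. Censoring already deals with incomplete follow-up. Deleting these subjects instead removes only non-events from the risk sets, so the estimated resolution rate rises in any arm that has dropout. If dropout differs between arms, the rise differs too, and the hazard ratio moves away from its true value.

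Two uses of the PP set suffer:

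- Protocol 11.4.3.1 says the PP repeat is there to show the effect of the analysis population and of additional nitazoxanide. The clause adds a third, outcome-driven difference, so a gap between PP and mITT cannot be read as intended.
- The PP worst-case analysis re-censors dropouts at Day 180, but the PP definition has already removed essentially all of them. That half of SAP Table 17 therefore cannot reveal the problem.

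**Working it through.** **Inputs.** Medians of 135 and 67.5 days, 64 per arm, and 20% attrition (SAP 5); 180 days of follow-up (SAP 3.2.1); two-sided 5% (protocol 11.1); 31 enrolled (SAP 14.2). *Assumed:* exponential resolution and dropout times, dropout independent of resolution, and dropout by arm varied over a range, because the documents give only 20% overall.

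**The plan's own figure.** The plan states that "a sample size of 64 subjects in each arm (128 total) is required to achieve 90% power using the Log-Rank test". The chance of resolution by Day 180 is 1 − 2^(−180/135) = 0.603 on placebo and 1 − 2^(−180/67.5) = 0.843 on nitazoxanide, mean 0.723. Expected events are 128 × 0.723 = 92.5. Power is Φ(√92.5 × ln 2 / 2 − 1.96) = Φ(1.37) = 91.5%, close to the 91.3% in the plan's 0%/0% cell. Inflation: 64 / 0.8 = 80 per arm. The model matches the plan's.

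**Who is kept, and the PP median.** Let λ = ln 2 / median, μ = −ln(1 − d)/180 for dropout d by Day 180, and s = λ + μ.

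- Share kept: K = (λ/s)(1 − e^(−180s)) + e^(−180s).
- PP median m solves (λ/s)(1 − e^(−sm)) = K/2.

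With d = 20%:

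- Placebo: λ = 0.005134, μ = 0.001240, s = 0.006374. K = 0.8055 × 0.6825 + 0.3175 = 0.867. m = −ln(1 − 0.4336/0.8055)/0.006374 = 121.3 days, against 135.
- Nitazoxanide: λ = 0.010269, s = 0.011508. K = 0.8923 × 0.8740 + 0.1260 = 0.906. m = −ln(1 − 0.4529/0.8923)/0.011508 = 61.6 days, against 67.5.

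Also requiring diaries through Day 60 (dropout time beyond Day 60) gives 123.4 and 63.4 days.

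**Hazard ratio with no true effect.** In the PP set the hazard is λ/K at Day 0 and falls to λ at Day 180. With both medians 135, 10% dropout gives K = 0.934 and 30% gives K = 0.799. For 10% placebo and 30% nitazoxanide, the hazard ratio runs from 0.934/0.799 = 1.17 at Day 0 to 1.00 at Day 180. The Cox estimate averages over this range, at about 1.11 to 1.12.

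Simulation (10,000 runs, unstratified log-rank test at 5%, median hazard ratio, both medians 135):

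| Dropout, placebo/nitazoxanide | mITT, N=160 | PP, N=160 | PP with diary rule, N=160 | PP rejection, N=31 |
|---|---|---|---|---|
| 20/20 | 1.00, 4.9% | 1.00, 4.9% | 1.00, 4.8% | 5.6% |
| 10/30 | 1.00, 5.1% | 1.11, 8.2% | 1.09, 7.6% | 5.5% |
| 30/10 | 1.00, 5.1% | 0.90, 7.9% | 0.92, 7.1% | 5.9% |
| 0/40 | 1.00, 5.1% | 1.24, 17.3% | 1.20, 13.7% | 8.4% |
| 40/0 | 1.00, 5.3% | 0.80, 18.4% | 0.84, 13.3% | 9.1% |

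With a true hazard ratio of 2.0, the PP set (without the diary rule) gives 2.15 for 10/30 and 1.77 for 30/10.

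**After the fix.** With the clause deleted and the Day 60 diary rule kept as written, the PP set holds everyone whose dropout time is beyond Day 60. That condition does not involve the resolution time, so under independent dropout the null hazard ratio returns to 1.00 and the medians to about 135 and 67.5.

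**The case against.** **Importance.** The PP set is secondary. The primary mITT analysis censors dropouts, and no decision is tied to PP. The trial stopped at 31 subjects, and SAP 14.2 calls the analyses primarily descriptive. Under the null about 0.603 × 31 = 19 events are expected, so the standard error of the log hazard ratio is about 2/√19 = 0.46; a bias of ln 1.11 = 0.10 is roughly a quarter of that. SAP Table 7 and Listing 5 would show unequal exclusions. All of this stands and limits the severity. It does not justify the clause: descriptive medians and hazard ratios are what readers will see, and their bias does not shrink with sample size.

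**Diary rule.** Read literally, it already removes anyone who stops well before Day 60, resolved or not. This also stands, and it weakens the bias from about 1.11 to about 1.09, but dropouts after Day 60 are still sorted by outcome.

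**Incomplete fix.** If the diary rule stays, early dropouts remain excluded. They do, but they are excluded whether or not they resolved, which adds no bias under independent dropout.

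**Stronger readings that the documents do not support.**

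- A reader might infer that PP removes every censored subject. Subjects unresolved at Day 180 are censored and expressly kept.
- A reader might infer that PP favours nitazoxanide. The bias favours whichever arm loses more subjects, and no dropout by arm is given.
- A reader might infer that the primary result is affected. It is not.

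**Conclusion.** The defect is real and moderate, and it is confined to the secondary PP analyses. The follow-up clause makes PP membership depend on the primary outcome. At the plan's 20% attrition in each arm, the PP medians fall by about 14 days (135 to 121) and 6 days (67.5 to 62), or to about 123 and 63.5 with the diary rule. The hazard ratio is distorted under the null only if dropout differs by arm: about 1.11 to 1.12 for 10/30 (1.09 to 1.10 with the diary rule) and about 0.90 (0.92) for 30/10. With 31 subjects the error rate hardly moves at those splits (5.5% to 5.9%), but the bias in the estimate is the same size.

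These sizes rest on exponential times, dropout independent of resolution, and assumed dropout splits. The dependence on outcome follows from the wording alone. If dropout is related to prognosis, censoring is not free of bias either, but the clause has no compensating benefit.

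**What to change.** 1. Delete the follow-up completion clause from protocol 11.4.2 and SAP 6.3.2.
2. Delete the SAP Table 7 row for incomplete follow-up and its entry in the priority note.
3. State that dropouts who remain in PP are censored at their last completed diary, as in SAP 6.5.

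Eligibility, product compliance and diary compliance still define the set. This also matches SAP 8.1.1, which describes PP exclusions only as diary and treatment non-compliance, and it gives the PP worst-case analysis subjects to act on.

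Subjects who fail the Day 60 diary rule stay out whether or not they resolved. If diary compliance is instead to be judged only up to resolution, it must also stop at the last diary for dropouts; otherwise outcome-dependent exclusion returns.

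The cost is one clause in each document, one table row and part of a note, with no new data. Enrolment has closed, but the SAP preface allows deviations to be recorded in an amendment or the study report. If the database is already locked, report the corrected PP analysis as supplementary, beside the one as written.

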6.3.3. Safety Population

The safety population (grouped by actual treatment received) will include all subjects who are randomized, have received at least one dose of study treatment. This analysis set will be used for all safety analyses.

6.3.4. Immunogenicity Population

The immunogenicity population will include all randomized subjects who received at least one dose of assigned study drug and have at least one stool and/or serum immunoglobulin test result. This analysis set will be used for all immunogenicity analyses.

6.4. Covariates and Subgroups

As described in Section 4.4.3, the randomization of treatment assignments and the primary analysis will be performed as stratified by duration of symptoms, transplant type, and age range.

The protocol also defines formal subgroup analyses as exploratory outcome measures; however, the study was not powered to perform these subgroup analyses. Subgroup sensitivity analyses for the primary and secondary outcome measures will evaluate the treatment effect across the following subgroups:

- Additional nitazoxanide: Subjects that took additional nitazoxanide (defined as in Section 3.3) will be excluded from the analyses
- Chromaturia: Subjects with unsolicited self-reported chromaturia (discoloration of urine) will be excluded from the analyses.

[Listing 22](#) and [Listing 11](#) provide listings of subjects that reported chromaturia or took additional nitazoxanide, respectively.

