stock and not provided by the study. Additional stool specimens should be collected prior to initiation of therapy for testing in the central lab when feasible.

The study will have 2 phases:

1. Treatment Phase (Study Day 1-28)
2. Longitudinal Monitoring Phase (Study Day 29-180)

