11.4.3 Efficacy Analyses

11.4.3.1 Analysis of Primary Outcome Measure

The primary efficacy outcome measure is the time from randomization to initial clinical resolution of Norovirus for at least 48 hours, assessed through 180 days, in each study arm. Clinical resolution will be assessed from the daily diary by the subject and will be defined as:

- a. Cessation of vomiting and
- b. No stools classified by the Bristol Stool Chart as diarrhea (Type 6 or 7)

The primary efficacy outcome measure will be assessed in the mITT population. Subjects who receive additional treatment with nitazoxanide other than their assigned study product will be considered censored at 180 days. To assess the effect of the choice of analysis population and additional treatment, the analysis will be repeated as a secondary analysis in the PP population. Sensitivity analyses may be performed to further assess the effect of additional treatment. The details of any sensitivity analyses will be detailed in the Statistical Analysis Plan.

The null hypothesis that the time to first clinical resolution of Norovirus is the same in both treatment arms will be tested using a stratified Log-Rank test to take into account the stratification at randomization. Estimates for median time to resolution and corresponding 95% confidence intervals will be reported for each treatment arm.

We will consider 80% compliance across the monitoring period acceptable [missing no more than 1.5/7 days per week over an 8 week period]. While we will not exclude patients, who are below this compliance for any monitoring period, we will conduct a sensitivity analysis comparing those with few missing values to those with 2 or more missing values per week.

With respect to missing data for the primary endpoint, the primary analysis will be handled as follows:

- Data that are missing after a subject has reached clinical resolution will not affect the primary time to event analysis and therefore will be ignored
- Subjects who drop out, are lost to follow-up, withdraw consent, or otherwise stop completing daily diary entries before clinical resolution will be censored on the day of their last completed diary
- Subjects with a gap in outcome data prior to clinical resolution will be handled depending on their last completed diary entry and their next completed diary entry:

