8.2. Secondary Efficacy Analyses

The secondary efficacy outcome measures are as follows:

- The time from randomization to first negative viral load through 180 days.
- The change in viral titer between Day 1 and Day 180.

The protocol calls for a Log-Rank test to compare time from randomization to first negative viral load through 180 days between the nitazoxanide treated group and the placebo group; however, due to early closure of the study, the number of subjects is too small to use a Log-Rank test. Number and percentage of subjects with positive viral load and geometric mean viral titer in positive subjects with 95% confidence intervals will be presented by test type, treatment group and study day in the mITT Population ([Table 20](#)). A stratified Cox proportional hazards model will be used to compare treatment to control through Day 180 with respect to time to first negative viral load. Stratification will be based on acute versus chronic symptoms at baseline. GII and GI test types will be analyzed independently.

The analysis will be conducted in both the mITT population and the PP population. The treatment hazard ratio estimate, 95% confidence interval and p-value from the likelihood ratio test will be presented for each test type ([Table 21](#) and [Table 22](#)). The median time to clinical resolution and 95% confidence interval will be summarized by treatment arm and duration of symptoms for each test type. In addition, stratum-specific estimates of the treatment hazard ratio within each duration of symptoms strata will be presented for each test type. Kaplan-Meier curves for each treatment arm will be displayed in [Figure 10](#), [Figure 11](#), [Figure 12](#) and [Figure 13](#), for each test type in the mITT and PP populations. [Figure 14](#) and [Figure 15](#) will present Kaplan-Meier curves for each treatment arm and duration of symptoms strata for Norovirus GII and Norovirus GI test types, respectively, in the mITT population.

The analysis will be repeated on the mITT population using the subgroups defined in Section [6.4](#) for each test type ([Table 23](#) and [Table 24](#)).

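### SAP 6.4 tests robustness to additional nitazoxanide by dropping re-treated subjects, which selects on a post-randomisation event that the plan itself ties to poor clinical outcome

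*SAP*

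**What the plan says.** Additional nitazoxanide is discouraged but allowed after Day 28 when the local investigator attests medical urgency (Protocol 7; SAP 4.4.7). The plan handles it differently by endpoint.

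- **Clinical primary.** Protocol 11.4.3.1: "Subjects who receive additional treatment with nitazoxanide other than their assigned study product will be considered censored at 180 days". SAP 5 uses the same rule for its power grid. SAP 8.1 does not restate it, and SAP 6.5 limits imputation to missing diary data.
- **Virologic endpoints.** SAP 8.2 fits a Cox model to "compare treatment to control through Day 180 with respect to time to first negative viral load" and an ANCOVA to the Day 1 to Day 180 titre change. Neither SAP 3.3 nor 8.2 says what happens to results obtained after additional nitazoxanide. The mITT analysis follows randomised assignment (SAP 6.3.1).
- **Sensitivity analysis.** Protocol 11.4.3.1 leaves sensitivity analyses of additional treatment to the SAP. SAP 6.4 provides one: "Subjects that took additional nitazoxanide (defined as in Section 3.3) will be excluded from the analyses". SAP 8.1.1 and 8.2 apply it in Tables 18, 23, 24, 27 and 28.
- **Who is re-treated.** SAP 5 assumes that "subjects who would have the worst study outcomes (longest time to clinical resolution of diarrhea) will be the most likely to receive additional treatment".
- **Per protocol.** A subject re-treated before the primary clinical outcome is excluded (Protocol 11.4.2; SAP 6.3.2). SAP 8.2 also runs the virologic endpoints in this population.

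**The concern.** Re-treatment happens after randomisation and depends on how the subject is doing. Removing re-treated subjects breaks the randomised comparison. If they are mainly slow resolvers, the arm that is re-treated more loses more of its poor outcomes and looks better than it is. The result would be read as a robustness check, yet it can move in either direction with no change in the true effect.

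The per-protocol analysis does not repair this. For re-treatment before clinical resolution it makes the same kind of exclusion. For a subject who resolves, relapses and is re-treated while still PCR-positive, it makes none, and later clearance counts for the randomised arm.

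The virologic analyses also answer a different question from the primary without saying so. The primary treats re-treatment as failure to Day 180; the virologic analyses ignore it.

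**Working it through.** **Inputs.** Two-sided 5% log-rank test (Protocol 11.1: "The test for primary efficacy hypothesis will be conducted using a Log-Rank test at the 5% two-sided level of significance"). From SAP 5: "a sample size of 64 subjects in each arm (128 total) is required to achieve 90% power using the Log-Rank test"; "The median diarrhea duration for the placebo group is assumed to be 135 days"; nitazoxanide median 67.5 days. Follow-up is 180 days. Exponential times are assumed, so the true resolution HR is 135/67.5 = 2.0. Rates below are placebo/nitazoxanide.

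**Step 1: reproduce the plan.**
- Probability resolved by Day 180: placebo 1 − 2^(−180/135) = 0.603; nitazoxanide 1 − 2^(−180/67.5) = 0.842; mean 0.723.
- Freedman events: [(1+2)/(1−2)]² × (1.960+1.282)² = 9 × 10.51 = 94.6. N = 94.6/0.723 = 130.8, close to the stated 128.
- 128/0.8 = 160.
- SAP Table 2, simulated at 64 per arm with the longest times in each arm censored at Day 180:

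| Re-treated (placebo/nitazoxanide) | Stated power | Simulated |
|---|---|---|
| 0/0% | 91.3% | 91.2% |
| 15/10% | 91.2% | 91.5% |
| 20/20% | 87.1% | 86.8% |
| 25/25% | 73.9% | 74.0% |
| 30/30% | 40.9% | 40.6% |

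The stated power therefore belongs to the Day-180 rule with the slowest subjects re-treated.

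**Step 2: what exclusion does, by hand.** Suppose the slowest fraction r of an arm is dropped. The proportion resolved by Day 180 becomes (original proportion)/(1 − r), capped at 1.
- No exclusion: 60% against 84%.
- 15/5%: 0.603/0.85 = 71% against 0.842/0.95 = 89%.
- 30/5%: 0.603/0.70 = 86% against 89%. The difference almost disappears.
- 20/20%: 0.603/0.80 = 75% against 100%. Only 15.8% of the nitazoxanide arm is unresolved at Day 180, so dropping 20% removes every failure.

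**Step 3: hazard ratios for a true HR of 2.** Large-sample Cox simulation, 200,000 per arm, censored at Day 180. Strict selection re-treats the slowest subjects. Weaker selection re-treats at random among subjects still unresolved at a time uniform over Days 29 to 90.

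| Re-treated | Exclusion, strict | Exclusion, weaker | Day-180 rule, strict | Day-180 rule, weaker |
|---|---|---|---|---|
| 15/5% | 1.76 | 1.88 | 2.00 | 2.13 |
| 20/5% | 1.59 | 1.80 | 2.00 | 2.24 |
| 30/5% | 1.22 | 1.65 | 2.00 | 2.48 |
| 20/20% | 2.76 | 2.06 | 1.86 | 1.76 |

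Under strict selection the Day-180 rule returns 2.00 largely by construction, because 39.7% of placebo is unresolved at Day 180 anyway.

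**Step 4: no true effect.** At 64 per arm, both medians 135 days, strict selection, exclusion rejects (two-sided) in about 21% of trials at 20/10% and 55% at 30/10%, nearly all favouring placebo, and in 12% at 20/20%. The Day-180 rule stays at about 5%. Under weaker selection that rule gives an HR of 1.12 to 1.32 from 15/5% to 30/5%, favouring nitazoxanide.

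**Step 5: the trial as run.** For 31 subjects, expected events are 31 × 0.723 = 22.4 and SE(log HR) ≈ 2/√22.4 = 0.42. An HR of 2.0 then has a 95% CI of about 0.87 to 4.6.

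**The case against.** **The size depends on who is re-treated.** SAP 5 says the worst-outcome subjects are the most likely to be re-treated, not that exactly the slowest are. With re-treatment random among subjects unresolved at Day 28, exclusion gives 1.94, 1.89 and 1.81 at 15/5%, 20/5% and 30/5%, and 2.01 at 20/20%. The Day-180 rule gives 2.19, 2.33, 2.69 and 1.74, further from 2 in every cell. This stands. It rules out presenting the Day-180 rule as the unbiased answer. It does not rescue the exclusion, whose error depends on a selection mechanism that the data cannot show.

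**A reader might infer that the main virologic analyses are wrong, or biased toward no difference.** The documents do not support that. Counting all results by randomised arm is the treatment-policy analysis implied by the mITT definition. The direction is not fixed either. If clearance follows the clinical medians, the slowest are re-treated over Days 29 to 90 and they then clear at the active-arm rate, the HR is 1.76, 1.64 and 1.42 at 15/5%, 20/5% and 30/5%. If instead re-treatment at Day 45 or 90 divides the remaining time by 2 to 4, it is 1.63 to 2.02 at 30/10% and 2.48 to 3.05 at 20/20%.

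**A reader might infer that exclusion is the only handling beyond the primary's rule.** It is not: the per-protocol analysis is a second, though imperfect, one.

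**The extension to virology is an inference.** SAP 5 speaks of clinical resolution. The documents give no clearance-time distribution, and Protocol 2.1 describes symptom resolution with continued shedding. Re-treated subjects may also be early resolvers who relapsed. This stands.

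**Materiality.** The SAP was finalised after enrolment stopped at 31, and SAP 14.2 calls the analyses primarily descriptive. At about 15 per arm, 15/5% is roughly two subjects against one. This stands, although SAP 8.1 and 8.2 still report hazard ratios, confidence intervals and p-values.

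**Conclusion.** The concern holds for the sensitivity analysis. Dropping re-treated subjects selects on a post-randomisation event that SAP 5 ties to the worst clinical outcomes, and the per-protocol analysis does not correct it. With more re-treatment on placebo (15/5% to 30/5%), a true HR of 2 becomes about 1.76 to 1.22 under strict selection and about 1.88 to 1.65 under weaker selection. At 20/20% under strict selection it becomes about 2.8. These figures rest on exponential times with the plan's clinical medians; applying them to viral clearance is an assumption.

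For the main virologic analyses the defect is narrower: the strategy is legitimate but undeclared, and it differs from the primary's. A reader might want the Day-180 rule as the main virologic analysis. Under weaker selection that rule gives about 2.1 to 2.5 for a true HR of 2 when placebo is re-treated more, so it belongs in a supportive role. With 31 subjects, a shift from 2.00 to 1.76 is small beside an interval of 0.87 to 4.6. The gain is in interpretability.

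**What to change.** 1. **SAP 6.4 and 8.1.1 (Table 18).** Replace the additional-nitazoxanide exclusion with a treatment-policy analysis of the primary in all mITT subjects, using outcomes as observed whatever additional nitazoxanide was taken. Restate the protocol's Day-180 rule in SAP 8.1, so that the two analyses are visibly different. Keep re-treated subjects as counts by arm (Table 6) and in Listing 11. The chromaturia subgroup is not affected.
2. **SAP 8.2.** Declare the main virologic analyses as treatment-policy. In Tables 23 and 24, replace the exclusion with a supportive analysis of time to first negative viral load: ignore results after the first additional dose, and treat subjects still positive then as not cleared, censored at Day 180. State beside it that this rule can favour nitazoxanide when placebo is re-treated more, and that it is to be read with the treatment-policy result.
3. **Tables 27 and 28.** Drop the additional-nitazoxanide rows or label them descriptive. I would not substitute an ANCOVA on the last stool before re-treatment. It would mix earlier samples with Day 180 samples, and the pre-therapy specimen is only requested, not assured (Protocol 7: "Additional stool specimens should be collected prior to initiation of therapy for testing in the central lab when feasible").

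The cost is SAP wording and reruns of existing models on collected data. No new data are needed and patient care does not change.
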